The fan technique consists in introducing the needle as for the retrograde technique, and injecting the gel while withdrawing the needle, without removing its tip from the skin; then, changing the direction of the needle and injecting a new line. Repeating this process several times will achieve a fan pattern. This technique allows filling a large area and creating or restoring facial volume from a single injection point.

Lateral movements of the needle must be avoided since these may result in a fanlike dissection of the sub-epidermal plane, increasing the incidence of local AEs like bruising, swelling, redness, pain, or tenderness at the injection site.

The device should be injected slowly with the least amount of possible pressure for the same reason. If the needle is blocked, the pressure on the plunger rod should not be increased, but the injection stopped and the needle replaced.

If a larger volume of the filler is needed to achieve the correction, small volumes should be injected in two sessions, instead of high volumes in one session.

The injection must be stopped just before the needle is pulled out of the skin to prevent leakage of the device or placement too superficially in the skin.

The remainder of the investigational device from the same syringe after application to one fold can be used for the application to the other fold of the same subject at the same visit but not for any other subject or any other visit of the same subject.

In case of a vascular event, injection must be stopped immediately, and high dose hyaluronidase, massage and heat (gauze with hot water) should be applied. In addition, nitroglycerin paste may encourage vasodilatation. More details are provided in Section 4.2.

Completion of administration

After injection the investigator may apply a light massage for uniform distribution of the filler.

Application of ice packs for 5-10 min. post injection is optional and may reduce redness and swelling.

The subject should be requested to stay in the office for several minutes after the injection, to detect possible blanching caused by arterial occlusions.

Prior to discharge the subject should be advised to follow restrictions specified in Section 6.3.7:

- To refrain from application of make-up for 12 hours after injection;
- To avoid prolonged exposure to sunlight or ultraviolet (UV) radiation for 36 hours after injection;
- Not to massage the treatment site for one week following the injection, to avoid the possible risk of
 product mobility;

• To abstain from use of saunas or Turkish baths for one week after the injection.

6.2.3 Applied volume of the device

The amount of the device injected will depend on the defect to be corrected and will be selected by the investigator. The actual volume injected will be estimated by the investigator and recorded in the CRF, together with information on injection technique, area of application, date, and exact start time and end time of injection.

The maximum recommended dosage is up to 10 mL per treatment session and up to 20 mL per subject per year; these amounts include potential Touch-up treatments.

6.2.4 Touch-up treatment

A Touch-up treatment may be performed at the Week 2 visit at the investigator's discretion, if correction is not deemed satisfactory after the first injection. It will be documented in the CRF with the same level of details as the initial treatment.

6.2.5 Precautions

- The device must not be used if the expiry date has lapsed, or if the packaging or contents are damaged.
- The device should only be used with the needle and syringe provided by the manufacturer.
- The needle must not be manipulated or bent, if the needle is blocked, pressure on the plunger rod should not be increased, instead injection should be stopped and the needle replaced.
- After use the syringe, needle and remaining contents should be disposed appropriately and the device should never be re-used.
- The device should not be injected into blood vessels, bones, tendons, ligaments, nerves, muscles or naevi.
- Injections into the periorbital area (crow's feet, eye circle, eye lids), glabellar region and nasal alae are not recommended.
- Overcorrection should be avoided.
- The device should never be placed in contact with quaternary ammonium compounds (such as benzalkonium chloride solutions) or with medical-surgical instruments that have been in contact with these substances.

6.2.6 Rescue medication

In case of overcorrection or occurrence of nodules or vascular compromise, a commercially available hyaluronidase injection (e.g. **and the second and the second at the discretion of the investigator**.

6.2.7 Investigational device accountability

The investigational device must not be used outside the context of this clinical investigation plan (CIP).

Documentation of receipt, dispensing/use in individual subjects, and return of investigational device must be maintained by the investigator or his/her designee. Appropriate forms will be provided by the Sponsor or their representative to facilitate investigational device accountability.

At the end of the clinical investigation, all remaining supplies, including empty boxes of investigational devices that have been used, must be returned to the Sponsor for accurate accounting of the investigational device. Empty or used syringes will not be returned to the Sponsor, but will be destroyed by the investigation site, in line with their routine procedure for medical waste disposal.

Considering the number of subjects to be enrolled, the average volume of the device administered in the clinical investigation of Princess[®] VOLUME (0.9 mL per fold), and potential additional Touch-up

treatment, it is anticipated that approximately 300 units of the investigational device will be used during this clinical investigation.

6.3 Subjects

6.3.1 Number of subjects and duration of the clinical investigation

Up to 60 subjects with moderate to severe nasolabial folds will be enrolled and treated with the investigational device in order to obtain the Week 24 performance data in at least 40 subjects.

Each subject will participate in the study for 9 months. Taking into account the anticipated recruitment period of 3-4 months, the total expected duration of the clinical investigation will be 13 months.

6.3.2 Recruitment strategy

The recruitment over the study will be competitive and will be stopped as soon as 60 subjects are enrolled in the study. The study subjects will be recruited by the investigator, among subjects who attend the investigation site seeking the corrective treatment for nasolabial folds. The investigator may also offer participation in the study to potential candidates identified in their subject database. In case of an unexpectedly low recruitment rate, the investigation may be advertised. In such case, the advertising strategy and materials will be submitted to the Ethics Committee (EC) for prior review and approval.

6.3.3 Subject identification

The study participants will be assigned a unique 5-digit number, with the first two digits identifying the site and the last three digits identifying the subject, e.g. 01-001. At each site the investigator will assign numbers to subjects in ascending order e.g. 001, 002, 003 etc. See also Section 6.3.10 for subject's confidentiality.

6.3.4 Inclusion criteria

A subject must meet all of the following criteria to qualify for participation in this investigation

- 1. Male or female 18 years of age or older
- 2. Presence of two fully visible, approximately symmetrical nasolabial folds, with each of the folds scored 2-3 according to the 5-grade NLF-SRS as assessed by the investigator
- 3. Healthy skin in the facial area and free of diseases that could interfere in cutaneous aging evaluation
- 4. Willingness to abstain from any aesthetic or surgical procedures in the treatment area for the duration of the clinical investigation
- 5. Written signed and dated informed consent

6.3.5 Exclusion criteria

Subjects meeting anv of the following criteria should not be enrolled:

- 1. Pregnancy, lactation, planned pregnancy or unwillingness to use contraception at any time during the study (for women of child-bearing potential only)
- 2. History of mental disorders or emotional instability
- 3. History of allergic reaction or hypersensitivity to hyaluronic acid, lidocaine, or any amide-based anaesthetic
- 4. Presence of silicone implant or another non-absorbable substance (permanent fillers) in the nasolabial region
- 5. Facial surgery or implantation of dermal fillers, absorbable and non-absorbable sutures (thread), laser therapy, dermoabrasion, or botulinum toxin application in the nasolabial region within

previous 12 months, or chemical peeling within previous 3 months, or planning to undergo such procedures in the treatment area during the study

- 6. Presence of infectious, inflammatory, or proliferative lesions in the nasolabial region
- 7. Cutaneous lesions in the treatment area
- 8. Known human immune deficiency virus-positive individuals
- 9. History of allergies against aesthetic filling products and recurrent herpes simplex
- 10. Tendency to hypertrophic scars and/or keloid formation
- 11. History or presence of any autoimmune or connective tissue disease, or current treatment with immune therapy
- 12. Diabetes mellitus or uncontrolled systemic diseases
- 13. Use of anticoagulant, antiplatelet or thrombolytic medication from 10 days pre- to 3 days post injection
- 14. Any medical condition which, in the investigator's opinion, prohibits the inclusion in the study
- 15. Current or previous (within 30 days of enrolment) treatment with another investigational drug and/or medical device or participation in another clinical study
- 16. Previous enrolment in this clinical investigation
- 17. Subjects whose participation in clinical trials is prohibited by the Austrian Medical Devices Act (e.g., persons with a legal custodian appointed due to mental disability, prisoners, soldiers and other members of the armed forces, civil servants)

6.3.6 Withdrawal criteria and procedures

The subject may be withdrawn from the investigation for any of the following reasons:

- 1. Occurrence of an AE which requires a premature termination of the treatment or precludes followup of the subject
- 2. A major CIP deviation, which may interfere with evaluation of the treatment outcome (e.g., additional aesthetic correction of the defect during the course of the study, use of prohibited medication, or similar)
- 3. Investigator's decision, triggered by safety, behavioural or administrative reasons
- 4. Informed consent withdrawal

A subject is free to withdraw the consent and leave the investigation at any time with no obligation to specify the reason for withdrawal. Efforts should be made, however, to get in touch with subjects who did not attend the scheduled visit and clarify the reason for default.

Reasons, circumstances and findings related to early withdrawal should be fully described on the CRF respecting the subject's rights. Attempts should be made to perform an early termination visit, which should consist of the assessments planned for the Week 24 visit. In the event that the withdrawal is caused by an AE, the procedures stated in Section 14.6 must be followed.5

6.3.7 *Life-style and other restrictions*

Contraception

The safety of Princess[®] VOLUME Lidocaine for use during pregnancy has not been established, so females of childbearing potential should use contraception or avoid unprotected sexual intercourse throughout the clinical investigation. Any pregnancy occurring during the subject's participation in the investigation will be reported as an AE and followed-up as described in Section 14.6.

Other restrictions

The following restrictions apply to all subjects:

- Make-up should not be applied for 12 hours after injection;
- Prolonged exposure to sunlight or UV radiation must be avoided for 36 hours after injection; day
 care with UV protection should be used daily throughout the entire clinical investigation;
- To minimise the risk of product mobility, the subject should be advised to avoid massaging the treatment site or applying pressure to this area for one week following the injection;
- Subjects should abstain from frequent solarium visits;
- Subjects should abstain from alcohol on injection days.
- Use of saunas or Turkish baths is prohibited for one week after the injection.

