NLF-SRS grading of nasolabial folds⁰	X**		x	x	х
Urine pregnancy test ^d	X**				
Eligibility assessment	X**				
Treatment	Х	X§			
Photography	X**	X§	Х	х	Х
Pain assessment ^e	Х	xΩ			
GAIS assessment ^f			х	х	Х
Subject satisfaction ^g			Х	х	Х
Adverse events ^h	x***	Х	x	х	Х
Concomitant medication ^h	x***	х	х	х	х

* Includes screening and treatment.

** Prior to application of the investigational device

*** From beginning of the treatment onwards

- § Optional, to be done at investigator's discretion
- Ω To be performed only if Touch-up treatment occurred
- ^a Includes date of birth, sex, and race
- ^b All medication taken by the subject within the previous 10 days
- Performed by the investigator using the Nasolabial Folds Severity Rating Scale (NLF-SRS); the severity of the left and the right fold will be separately graded
- ^d In females of child-bearing potential only, including women who are postmenopausal for less than 12 months
- Evaluated by the subject immediately after injection and approximately 15 min. thereafter using an 11-point Numeric Pain Rating Scale
- ^f Evaluated by the investigator using the Global Aesthetic Improvement Scale (GAIS)
- ^g Evaluated by the subject
- ^h To be collected throughout the investigation, from beginning of the treatment until the last visit

List of abbreviations

ADE	Adverse device effect
AE	Adverse event
BDDE	1,4-butanediol diglycidyl ether
CIP	Clinical investigation plan
CRF	Case report form
DCF	Data clarification form
EC	Ethics Committee
eCRF	Electronic Case report form
GAIS	Global Aesthetic Improvement Scale
GCP	Good clinical practice
HA	Hyaluronic acid
IB	Investigator's brochure
ICF	Informed consent form
MedDRA	Medical Dictionary for Regulatory Activities
mIU	Milli-international unit
NLF	Nasolabial fold
NLF-SRS	Nasolabial Folds Severity Rating Scale
NPRS	Numeric Pain Rating Scale
PT	Preferred term
SADE	Serious adverse device effect
SAE	Serious adverse event
SAP	Statistical analysis plan
SOC	System organ class
TMF	Trial master file
USADE	Unanticipated serious adverse device effect
UV	Ultraviolet
w/w	Weight/weight

Table of contents

Арр	Approval and signature pages		
Syno	opsis	5	
Sche	edule of procedures and events	8	
List	of abbreviations	9	
1	Background	. 13	
2	Identification and description of the investigational device	. 13	
2.1	Device description	. 13	
2.2	Manufacturer	. 14	
2.3	Intended use and mode of administration	. 14	
2.4	Traceability	. 14	

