2.1 Device description

Princess[®] VOLUME Lidocaine is a sterile, biodegradable, viscoelastic, clear, transparent, isotonic and homogenized injectable gel implant. The implant consists of hyaluronic acid obtained from *Streptococcus equi* bacteria, which is highly cross-linked using 1,4-butanediol diglycidyl ether (BDDE) and formulated to a concentration of 23 mg/mL in a physiologic buffer (phosphate buffer pH 6.8-7.4, sodium chloride) with supplementation of 0.3% w/w lidocaine hydrochloride.

The device packaging contains one prefilled syringe with 1.0 mL of the injectable gel implant, two 27G $\frac{1}{2}$ " disposable sterile needles and a product leaflet. A set of two labels showing the batch number is situated at the bottom of the box.

Princess[®] VOLUME Lidocaine is a class III medical device, which also contains an active pharmaceutical ingredient, a well-known local anaesthetic lidocaine hydrochloride, as an ancillary substance. It is an absorbable soft tissue filler for injection into the deep dermis and subcutis, and remains in long term contact with human skin and connective tissues. Hyaluronic acid is a natural component of human skin, hence Princess[®] VOLUME Lidocaine is naturally absorbed, with the lifetime of the device anticipated to last up to 9 months after treatment. The ancillary component, lidocaine

hydrochloride, is rapidly released from the device after injection, and due to short half-life of around 90 minutes is quickly eliminated from the body.

The device is manufactured in compliance with EN ISO 13485:2003/AC:2009. No materials of human or animal origin are used during manufacture or as raw materials.

Princess[®] VOLUME Lidocaine is designed for single use and upon opening should not be re-sterilized or reused.

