3.1 Safety Analysis Set (SAF)

The safety analysis set (SAF) consists of all subjects who have been treated with the investigational device.

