
4.5 Safety Analysis

Adverse events (AEs)

AEs will be coded by using the Medical dictionary for regulatory activities (MedDRA) version 19.1.

AEs will be tabulated by system organ class (SOC) and preferred term (PT). The number of entries, as well as the number and rate of affected subjects will be reported.

Deaths, SAEs and AEs with a causal relationship to the investigational device or procedure (definite, probable, possible or missing relationship) and AEs by intensity (mild, moderate, severe) are presented separately. Listings of adverse events leading to treatment discontinuation and those identified as "severe" will be provided.

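### Withdrawal under Protocol 6.3.6 can end the search for new AEs while the subject stays in the all-treated AE denominator, so later events can be under-counted

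*Protocol*

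**What the plan says.** Protocol 6.3.6 lists reasons for which a subject may be withdrawn from the investigation. Apart from withdrawal of consent they are:

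- "Occurrence of an AE which requires a premature termination of the treatment or precludes followup of the subject"
- "A major CIP deviation, which may interfere with evaluation of the treatment outcome", with an additional aesthetic correction and prohibited medication as examples
- "Investigator's decision, triggered by safety, behavioural or administrative reasons"

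The same section asks for an attempt at an early termination visit with the Week 24 assessments, which include AEs. It makes the 14.6 procedures mandatory when an AE caused the withdrawal. Section 14.6 follows AEs already identified, and pregnancies to their outcome.

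On the collection of AEs, footnote h of Table 1 says: "To be collected throughout the investigation, from beginning of the treatment until the last visit". Protocol 6.4.10 puts the end at Visit 5. On persistence of the gel, Protocol 2.1 describes absorption "with the lifetime of the device anticipated to last up to 9 months after treatment".

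In the SAP, the safety set (3.1) "consists of all subjects who have been treated with the investigational device", all safety analyses use that set (3.5), and for AEs "the number and rate of affected subjects will be reported" (4.5). Neither document plans a person-time or time-to-event summary of AEs. Nothing is imputed (SAP 4.6), and withdrawn subjects are not replaced (Protocol 6.1.5).

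**The concern.** These withdrawal rules suit a treatment that can be stopped. Here the product is placed on Day 0, with at most one touch-up at Week 2, so little treatment is left to terminate. Leaving the study removes the observer, not the gel.

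None of the three grounds makes a subject's later AEs uninformative. Yet no provision asks about new AEs after the subject has left, and the subject still counts in full in the denominator. In the AE table such a subject looks the same as one followed to Week 36 without an event. Any resulting bias in the rate of later events is downward.

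Occurrence and frequency of AEs is the only safety endpoint (Protocol 6.1.3). Protocol 4.2 states that this device has no human safety data so far, and 3.3 extends follow-up to 9 months to learn about long-term effects. Withdrawal for a deviation is also unnecessary, because the per-protocol set and the data review meeting already deal with deviators.

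**Working it through.** **Step 1. The plan's own figure.** The only quantitative planning figure is the half-width of a 95% interval for an expected proportion of 0.900: 0.076 at n = 60 (Protocol 7.1), and 0.076 to 0.093 for n = 60 to 40 (SAP, Number of subjects).

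- n = 60: 1.96 × √(0.9 × 0.1 / 60) = 0.0759
- n = 40: 1.96 × √(0.9 × 0.1 / 40) = 0.0930

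Both reproduce. They concern the success rate; there is no planning figure for AEs.

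**Step 2. Inputs for AEs.** From the documents: up to 60 treated, at least 40 with Week 24 data, AE follow-up to Week 36, all treated subjects in the denominator. Not in the documents, so assumed:

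- true 36-week risk p = 5% or 10%, at constant hazard
- share withdrawn w = 5%, 10%, 20% or 33% (3, 6, 12 or 20 of 60)
- withdrawal at week t = 2, 4, 12 or 24
- the same risk in withdrawn and retained subjects
- AEs up to withdrawal captured, as the early termination visit intends

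**Step 3. Formula.** Risk by week t: p(t) = 1 − (1 − p)^(t/36). Expected crude rate: (1 − w)p + w·p(t). Relative under-count: w × [1 − p(t)/p].

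Example with p = 10%, w = 10%, t = 4: p(4) = 1 − 0.9^(4/36) = 0.0116. The crude rate is 0.090 + 0.0012 = 0.0912. That is 5.47 affected subjects expected of 60, against 6.00 with full follow-up, or 8.8% fewer.

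**Step 4. Relative under-count at p = 10%** (the p = 5% results differ by at most 0.2 percentage points).

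| Withdrawn | at Week 2 | at Week 4 | at Week 12 | at Week 24 |
|---|---|---|---|---|
| 5% | 4.7% | 4.4% | 3.3% | 1.6% |
| 10% | 9.4% | 8.8% | 6.5% | 3.2% |
| 20% | 18.8% | 17.7% | 13.1% | 6.4% |
| 33% | 31.4% | 29.5% | 21.8% | 10.7% |

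In expected affected subjects, against 6.00: 5.81 with 10% withdrawn at Week 24, 4.94 with 20% at Week 4, and 4.23 with 33% at Week 4. If every event fell after withdrawal, p(t) = 0 and the relative under-count would equal w.

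**Step 5. What zero events would show.** The one-sided 95% upper bound is 1 − 0.05^(1/n): 4.9% with 60 followed, 5.4% with 54, 7.2% with 40. The chance of seeing at least one event of true risk 2% is 1 − 0.98^n: 70%, 66% and 55% respectively. A table with denominator 60 suggests the first figure of each set even if fewer were followed.

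**The case against.** A reader might infer that AE collection simply stops at withdrawal and that delayed events are under-counted as a matter of fact. The documents do not support that.

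- Withdrawal is discretionary, an early termination visit that includes AEs is to be attempted, and AE-caused withdrawal triggers mandatory 14.6 follow-up. For device-related SAEs that follow-up has no end-of-study cut-off. Only new, later events can be missed, and the gap is clearest for deviation and administrative withdrawals.
- That no new AEs are sought after withdrawal is read from the stated collection window and the absence of any other provision. It is not an explicit prohibition.

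A reader might also take the gap between 60 and 40 as 20 tolerated withdrawals. It equally covers recruitment below 60 (Protocol 7.1), consent withdrawal and loss to follow-up. Assigning all 20 to early investigator withdrawal is an extreme case.

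A 10% risk of late events is an assumption. Table 2 of the protocol lists nodules, granuloma, induration and discoloration as rare, and the documents give no onset times. At an assumed risk of 1% to 2% with 3 to 6 subjects withdrawn, at most 0.03 to 0.12 affected subjects are lost. Protocol 3.2 reports no long-term device effects in a 48-subject study of the same gel without lidocaine. Even 4 against 6 affected of 60 lies within sampling error: the exact 95% interval for 6/60 is 3.8% to 20.5%.

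SAP 4.1 already shows subjects available per visit and reasons for discontinuation. That makes the loss visible but does not correct the rate.

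These points limit the size. What stands against them is that the plan ends observation where it need not and then reports a rate as if observation were complete.

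**Conclusion.** The point holds in a conditional form. Later AEs can be under-counted, in one direction only, because withdrawal from the study is not separated from the end of treatment and the crude rate ignores time under observation.

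Under constant hazard and equal risk in withdrawn and retained subjects, the size is about 2% to 9% at 5% to 10% withdrawal, and up to about 31% in the extreme case of 20 of 60 leaving at Week 2. It would be larger if the events cluster late or if those withdrawn are at higher risk; the documents give no figure for either.

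The loss of Week 24 and Week 36 grades is a lesser matter. After another correction of the same fold, later grades no longer measure this device, so keeping such subjects in follow-up must not turn those grades into apparent benefit. The change is worthwhile because it is cheap, not because a large bias has been shown.

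**What to change.** **Protocol 6.3.6.** State that a major deviation, a treatment-stopping AE or an administrative reason leads to review for per-protocol exclusion, not to the end of follow-up. Unless consent is withdrawn or follow-up is impossible, the subject keeps the scheduled visits, or at least AE and concomitant-medication contact, through Week 36. This concerns observation only and alters no treatment rule.

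**Grades.** Record the date of any additional aesthetic correction; Protocol 6.4.11 already asks about such procedures at each visit. Flag NLF-SRS and GAIS grades after that date. State in SAP 4.3.1 that they are not counted as device effect in the primary summary, since the ITT analysis would otherwise take them in.

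**SAP 4.5.** Show the number of subjects under observation by visit beside the AE rates.

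**Cost.** The visits are already scheduled, and the per-protocol and data-review route exists (SAP 3.4 and 4.7). What is added is wording, a few extra contacts, and causality judgements for AEs after an outside procedure, which Protocol 14.4.2 already covers. If subjects are already enrolled, Protocol Section 9 may require renewed consent.

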6.4.11 Prior and concomitant medication and non-drug therapies

Prior medication is defined as all medication taken within 10 days (whether continuing or not) prior to Day 0. Concomitant medication is defined as all medication taken from Day 0 (including medication taken immediately pre-injection and post-injection) until the Week 36 visit.

At each visit the subject must be asked about any new medication taken or changes in current medication, as well as, about any aesthetic procedure applied in the area treated with the investigational device.

All prior and concomitant medication and non-drug therapies will be recorded in the subject's medical record and the CRF.

Prohibited medication and aesthetic treatments

- Immune therapy, i.e., treatment with biologics designed to boost the body's natural defences (from Day 0 until the end of the clinical investigation)
- Anticoagulant, antiplatelet, or thrombolytic drugs (from 10 days pre- until 3 days post-injection)
- Facial surgery or implantation of dermal fillers other than the investigational device (from 12 months prior to Day 0 until the end of the clinical investigation)
- Absorbable and non-absorbable sutures (thread), laser therapy or dermabrasion (from 12 months prior to Day 0 until the end of the clinical investigation)
- Botulinum toxin treatment in the area treated with the investigational device (from 12 months prior to Day 0 until the end of the clinical investigation)
- Chemical peeling (from 3 months prior to Day 0 until the end of the clinical investigation)
- Skin needling or mesotherapy (from Day 0 until the end of the clinical investigation)

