7.2 Analysed data sets

The primary data set for analysis will contain all data collected in the Intent-to-treat population, which is defined as all subjects who received the investigational device and have at least one post-treatment assessment. Certain sensitivity analyses may be also done in the Per-protocol population, which is defined as all subjects who received the investigational device and have completed the investigation without major CIP deviations.

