4.6 Missing Values

No missing value imputation methods will be applied.

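### A grade taken after the folds have been re-corrected by another procedure counts as this device's result in the primary ITT analysis, which can overstate the Week 24 and Week 36 effect

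*Protocol*

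**What the plan says.** **Purpose of the time points.** Protocol 3.3 places the primary endpoint at 6 months to address minimum durability and extends follow-up to 9 months for longer-term information. Section 2.1 describes the "lifetime of the device anticipated to last up to 9 months after" treatment, and section 4.1 speaks of an effect lasting 6 to 12 months.

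**Re-correction is foreseen.** Protocol 6.4.11 lists "Facial surgery or implantation of dermal fillers other than the investigational device" among the treatments prohibited until the end of the investigation. It also has subjects asked at each visit "about any aesthetic procedure applied in the area treated with the investigational device".

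**What happens to the subject.** Protocol 6.3.6 reads: "The subject may be withdrawn from the investigation for any of the following reasons". The second reason is a major deviation that may interfere with evaluation of the outcome, and its first example is "additional aesthetic correction of the defect during the course of the study". The section adds: "Attempts should be made to perform an early termination visit, which should consist of the assessments planned for the Week 24 visit".

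**What happens to the data.** Protocol 7.2 states: "The primary data set for analysis will contain all data collected in the Intent-to-treat population". SAP 3.2 and 3.5 make ITT the primary set with no exclusion for deviations. The modified ITT set (SAP 3.3) has none either. The per-protocol set (SAP 3.4) drops major deviators. SAP 4.6 states: "No missing value imputation methods will be applied"; Protocol 7.3 agrees. For continuous variables, the opening of SAP section 4 bases N on non-missing observations. For categorical variables, the default table in SAP 4.8 has a row for missing values inside a total of 100.0.

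**The concern.** Protocol 3.3 does without a control group because folds do not improve spontaneously, so change from baseline can be read as the effect of the device. That reasoning fails for a subject who has had another procedure on the same folds. Section 6.3.6 recognises this, but the recognition does not reach the primary analysis.

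A subject who seeks another correction because the effect has faded is evidence against durability. If that subject stays in the study and is graded, ITT records the grade after the other procedure as the device's own result, quite possibly as a response of at least 1 point. None of the three performance analysis sets treats re-correction as loss of effect. ITT and modified ITT keep the grade, and per-protocol leaves the subject out. The same applies to GAIS, subject satisfaction and the photographic review, since the photograph shows the result of the other procedure too.

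At stake is the credibility of a single-arm estimate whose primary time point was chosen to show that the effect lasts.

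**Working it through.** **1. The plan's own precision.** Protocol 7.1 (n = 60) and the SAP's sample size text (n = 40 to 60) assume a success proportion of 0.900 and a two-sided 95% interval by the normal approximation. Half-width = 1.96 × √(0.9 × 0.1 / n).

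- n = 60: 1.96 × √0.00150 = 0.0759, stated as 0.076.
- n = 40: 1.96 × √0.00225 = 0.0930, stated as 0.093.

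Both figures reproduce.

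**2. Which route a re-corrected subject is likely to take.** Table 1 has no visit between Weeks 4 and 24 or between Weeks 24 and 36. Procedures are asked about at visits (6.4.11). Contact between visits is requested only for untoward events (6.4.10). A re-correction at, say, Week 18 would therefore usually come to light at the Week 24 visit, where the NLF-SRS is graded anyway. If the subject is withdrawn earlier, the early termination visit also yields a grade after re-correction, and no rule says whether it counts as Week 24.

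**3. Effect of one retained subject.** If a subject would otherwise be a non-responder and is graded a responder after the other procedure, the proportion rises by 1/n: 1/40 = 2.5 points, 1/60 = 1.7 points. The shift exceeds the planned half-width at 4 such subjects when n = 40 (4/40 = 10.0 against 9.3 points) and at 5 when n = 60 (5/60 = 8.3 against 7.6 points).

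**4. A small example (counts assumed).** Week 24, 40 subjects, 3 re-corrected, 33 responders among the other 37:

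- retained and graded as responders: 36/40 = 90.0%;
- withdrawn without a grade, denominator restricted to observed grades: 33/37 = 89.2%;
- withdrawn without a grade, missing row kept within the total: 33/40 = 82.5%;
- counted as non-responders: 33/40 = 82.5%.

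**5. Range over the unknown rate.** Assume N = 60, k re-corrected before Week 24 and 0.90 success in the others (expected values, so counts need not be whole). Retained = (0.9(60 − k) + k)/60. Counted as non-responders = 0.9(60 − k)/60. The last column supposes that half of the k subjects would still have met the criterion without the other procedure.

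| k | Retained as responders | Missing, removed from denominator | Missing, kept in denominator, or counted as non-responders | Half would still have responded |
|---|---|---|---|---|
| 3 | 0.905 | 0.900 | 0.855 | 0.880 |
| 6 | 0.910 | 0.900 | 0.810 | 0.860 |
| 12 | 0.920 | 0.900 | 0.720 | 0.820 |

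If 90% of the re-corrected subjects would still have responded, the true rate is 0.900 and removing them causes no bias.

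**6. Mean change (values assumed).** Change is visit minus baseline, so improvement is negative. Take N = 60 and k = 6, with a mean of −1.2 in the others, −1.5 after the other procedure, and 0 had the re-corrected subjects been left alone.

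- Retained: (54 × −1.2 + 6 × −1.5)/60 = −1.23.
- Removed: −1.20.
- Without the other procedure: (54 × −1.2 + 6 × 0)/60 = −1.08. With −0.5 in place of 0 it is −1.13.

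**The case against.** A reader might infer that re-correction inflates durability by whichever route the subject takes: withdrawn subjects leave the denominator and retained subjects count as successes. The documents do not support that much.

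- **Denominator.** The responder endpoints are reported in frequency tables, and the SAP 4.8 default keeps missing values inside the 100.0 total. On that format a withdrawn subject without a grade counts exactly as a non-responder would (33/40 in the example). Appendix A, which describes the individual tables and may override the default, is not in the text available. Only the mean change clearly loses the subject.
- **Direction.** The GAIS category for improved describes a subject with obvious improvement for whom retreatment is still indicated (Protocol 6.4.6). Wanting another procedure therefore does not prove loss of a 1-point response.
- **Timing.** Protocol 3.2 reports an effect beyond 9 months for the version without lidocaine, and the sample size text assumes 0.900 success at Week 24. Fading is easier to expect by Week 36, a secondary time point.
- **Frequency.** Inclusion criterion 4, exclusion criterion 5 and the prohibited list all discourage re-correction, so it may be rare.
- **Oversight.** A data review meeting classifies deviations before lock, and the ITT and per-protocol results can be compared.

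The first four points stand and limit the claim. The last helps little: SAP 4.7 has the meeting allocate subjects to analysis sets, but gives it no rule for the grade itself. The comparison of ITT with per-protocol sets a credited grade against an excluded one, and neither counts the event as loss of effect.

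**Conclusion.** The gap is real. Under the stated ITT rule, a subject who is re-corrected and then graded, at a scheduled visit or possibly at an early termination visit, contributes the result of another procedure as this device's result. The responder rate and the mean improvement can be overstated.

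The bias is upward only on a condition. For retained subjects, the other procedure must have improved the grade. For subjects left out, they must have been going to do worse than the rest. It does not follow that every route overstates the responder rate, because the denominator for withdrawn subjects is unsettled.

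The size cannot be fixed, since the documents give no re-correction rate. Each retained subject who would otherwise be a non-responder adds 2.5 points at n = 40 or 1.7 at n = 60. One or two would matter little. Four at n = 40 or five at n = 60 would exceed the planned half-width. No formal test is affected, because the study is descriptive. This is a cheap improvement that should be made, because the Protocol foresees the event and already asks about it.

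**What to change.** **SAP 4.3.1, 4.3.2 and 4.4**

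- For the endpoints of at least 1 and at least 2 points, count a subject as a non-responder at every visit after any additional aesthetic correction of the treated area. State that the Week 2 Touch-up is part of the regimen and is not re-correction.
- State that the responder denominator keeps these subjects.
- Add a sensitivity analysis that excludes grades after re-correction or uses the last grade before it.
- Show the mean change with and without grades taken after re-correction.
- Say whether an early termination grade counts as Week 24.
- Report how many subjects were re-corrected before each visit.

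**Protocol 6.3.6**

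- Continue data collection and safety follow-up after re-correction unless consent is withdrawn. This concerns what is recorded, not how the subject is treated.

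**Cost.** A few sentences in the SAP and a small Protocol wording amendment, signed by the sponsor and investigators if section 9 applies. Procedures in the treated area are already asked about at each visit, so the main requirement is that the date be recorded. The responder rate may be slightly lower. Some subjects who still had a 1-point effect will count as failures, which the sensitivity analysis will show. Adverse events after another procedure will be harder to attribute.
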